Providing targeted education and support to women in the postnatal period through a mobile social network holds potential to improve postnatal recovery, neonatal care practices, nutritional status, general health, knowledge and care seeking - positively impacting maternal and child health. Mobile support and education groups are based on prominent health behavior change theories such as the capabilities and motivation constructs of the COM-B framework,^{18,19} and have positively impacted a variety of other health outcomes in both developed and developing world settings.^{2,10} Targeted interactive education and support to women in the postnatal period through a mobile social network is hypothesized to meet their knowledge needs, improve self-efficacy and maternal mental health, and alter perceived social norms. All of these are important for appropriately identifying infant and maternal danger signs and timely care seeking for routine and emergency visits (including referrals), and reduce infant and maternal mortality and morbidity (**Figure 1**). Furthermore, mHealth group support could help encourage and sustain exclusive breastfeeding, and improve uptake of postnatal family planning and childhood vaccination, which positively impact maternal and child health in both short and long term. The social support component will encourage free discussion, allowing women to share experiences and tips for success (advice on soothing a crying baby, balancing family obligations with caring for her own healing body, etc.), providing informational social support. Interventions targeting informational and emotional social support have previously resulted in improved maternal and neonatal health, including reduced postnatal depression^{36,37}.

Figure 1. Conceptual Framework of MeSSSSage Intervention Targets and Outcomes

Innovation. The approach taken in this research will add to the scientific understanding of whether mHealth interventions can successfully include group components and interaction between users. It will also expand our toolkit of approaches for intervening in the postnatal period, with applications for other times in the life course and populations. If proven successful, this study will lead to the development of a tested tool ready for next steps in the scale up process to robustly test effectiveness. It extends the current evidence in two primary ways:

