In-depth interviews: Additionally, in-depth interviews (IDIs) will be conducted with a selection of 10 women from each intervention condition (30 IDIs), purposively sampled based on high/low participation rates determined by the end line survey. We will collect data on experiences with *MeSSSSage* and how to improve it.

Technology assessment: Finally, we will collect and analyze the quantitative backend data from the prototype to gain more insight into women's participation in the intervention, including attendance and level of participation

in group interactive educational sessions, use of mobile social support platform (number of posts, frequency, topic), etc. Text data from transcripts of the educational sessions and content of group messaging will be analyzed for content in order to understand primary educational needs and interests for postnatal women.

Group moderator survey and interview: ASHA facilitators moderating the groups will be asked to respond to a short questionnaire after each group session to understand: preparation and delivery time, content, efficiency, acceptability and satisfaction with the group model, perspectives of impact, challenges, and any follow-up/referral necessary.⁴⁰ Regarding facilitation of groups that receive the text-based messaging intervention component only, ASHA facilitators will report on experiences in the prior week. We will conduct monthly semi-structured interviews with each of the ASHA facilitators to understand their preferences for group components, experiences preparing for and conducting the sessions, and their perspectives on mobile provision of education, care, and support.

Measures: The baseline survey content will include sociodemographic characteristics and knowledge about maternal and infant health, self-efficacy, and perceived social norms regarding MCH-related health promoting behaviors. The endline survey will include acceptability questions such as women's satisfaction with and perceptions of *MeSSSSage*, maternal and infant knowledge-, behavior-, and health-related questions including about breastfeeding, complementary food introduction, immunization, family planning uptake, maternal physical and mental health, etc. which have previously been used in this setting (Table 3)⁴.

Table 3: Participant survey measures (Phase 2)

Category	Measures

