Sociodemographic characteristics	Age, age at marriage, educational attainment, caste, language spoken, household assets, women's status/decision-making, social support and relationship quality.
Health-related knowledge (effectiveness)	Knowledge on maternal and neonatal danger signs, best practices for infant care, family planning.
Health-related behaviors (effectiveness)	Breastfeeding and complementary food introduction practices (breastfeeding initiation, length of exclusive breastfeeding, length of breastfeeding, timing of complementary food introduction), appropriate management of early childhood illnesses.
Health outcomes (effectiveness)	Early childhood immunization, postnatal depression and anxiety, postnatal family planning adoption.
Intervention perspectives (feasibility, acceptability)	Self-reported engagement in intervention components and topics, satisfaction with intervention components, likelihood of participating again, likelihood of recommending program, value on knowledge and social support gained from participation.

Analysis. *Aim 2. Feasibility and acceptability of the optimized MeSSSSage intervention components.* We will use a mixed methods approach, triangulating data from quantitative baseline and endline data, qualitative IDIs, and technology assessment. Feasibility and acceptability will be measured by participation rates at each session, participation trajectories over time, and user engagement (via technology assessment backend data). Women's reports of use and satisfaction (survey and IDI will shed light on barriers and facilitators to participation. Moderator acceptability will be assessed by satisfaction, fidelity to topic/content based on protocol and perspectives on impact. We will test for differences in feasibility and acceptability between the three intervention arms to understand if both components (group meetings and text) or only one is the best approach, using ANOVA for continuous outcomes and chi-square or Fisher's exact tests, as appropriate, for categorical outcomes.

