Aim 3. Preliminary effectiveness of the MeSSSSage intervention components on six-month MCH outcomes. Using the quantitative survey data, we will statistically evaluate differences by study arm in improvements in women's knowledge, behaviors, and maternal and child health outcomes, compared to the control group (including effect sizes, controlling for relevant socio-demographics as necessary). Figure 1 displays the outcomes that are theoretically related to our intervention targets. Our main *knowledge* outcome will be a composite score representing the proportion of correct answers from a knowledge scale on breastfeeding, newborn and infant care, maternal and infant danger signs, newborn care, and family planning, topics that will be covered within our interactive educational group component. Our main *behavior* outcome will be self-reported exclusive breastfeeding at 6 months. Our main *health related* outcomes will be: (1) completion of early childhood immunization schedule; and (2) postnatal family planning uptake. We will measure women's social support and related mental health status (depression and anxiety) using scales that have been previously validated in similar populations such as the Hopkins Symptom Checklist⁴¹ and the Multidimensional Scale of Perceived Social Support⁴². Finally, women's empowerment will be measured using decision-making and mobility scales.^{43,44}

Sample Size. This pilot development study is not formally powered to detect significant differences in outcomes, but will give insight into directionality of changes. The per group sample size was selected based on feasibility

of recruitment, intervention delivery, and the interpersonal interaction important for a group-focused intervention. The sample is sufficiently large to assess the feasibility and acceptability outcomes through descriptive statistics.

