Where y_i is the outcome for the i^{th} participant, β_0 is the coefficient for the intercept (standard of care), β_1 represents the mean difference in factor 1 (voice), β_2 represents the mean difference in factor 2, (text) β_3 represents the interaction between factor 1 and factor 2 (voice + text), Z_{1i} is the indicator variable for factor 1, Z_{2i} is the indicator variable for factor 2, and ε_i is the residual for the i^{th} participant. Due to the modest sample size, significance testing will be deemphasized and we have not included power analyses for this study.

Hypotheses for preliminary/exploratory analyses on effectiveness. Exploratory hypotheses will be evaluated as part of the study feasibility assessment process. Means and proportions will be plotted by group over time to enable descriptive evaluation of overall patterns of change across time in the outcomes for the intervention and control groups. For example, we expect that following intervention exposure, relative to control group participants, intervention participants will have improved health-related knowledge, health-related behavior, and health outcomes. We also anticipate that intervention participants receiving both voice and text components will have the highest report of the prior outcomes and reported social support, and we will explore differences in these outcomes and in levels of reported social support between the groups as described above.

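### Self-efficacy and perceived social norms, which the intervention is meant to change, have no endline measure in the plan, and the time point for social support and decision-making is left in conflict

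*Protocol*

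**What the plan says.** The Significance section of the Protocol gives the mechanism. Interactive education and support through a mobile social network "is hypothesized to meet their knowledge needs, improve self-efficacy and maternal mental health, and alter perceived social norms".

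The Measures paragraph (Approach, Phase 2) then divides the content between two surveys. For baseline: "The baseline survey content will include sociodemographic characteristics and knowledge about maternal and infant health, self-efficacy, and perceived social norms". For endline it names acceptability questions and "maternal and infant knowledge-, behavior-, and health-related questions including about breastfeeding, complementary food introduction, immunization, family planning uptake, maternal physical and mental health, etc", with a pointer to Table 3.

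Table 3 has no column for time point. Its sociodemographic row, the only one not tagged as effectiveness or as feasibility and acceptability, ends with "household assets, women's status/decision-making, social support and relationship quality".

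The Aim 3 analysis concerns preliminary effectiveness of the "intervention components on six-month MCH outcomes". It commits to the Multidimensional Scale of Perceived Social Support and to a symptom checklist for depression and anxiety, and adds: "Finally, women's empowerment will be measured using decision-making and mobility scales". Aim 3 in the Specific Aims also names empowerment.

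The SAP's paragraph on preliminary effectiveness, which repeats the Protocol's Statistical Design and Power section, lists knowledge, behaviours and health outcomes. It names none of the four constructs. Its hypotheses paragraph nevertheless expects the voice-plus-text arm to report the most social support, and says "we will explore differences in these outcomes and in levels of reported social support between the groups as described above".

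**The concern.** An arm difference after exposure needs a measurement after exposure. For self-efficacy and norms the plan names only a survey taken around enrolment, and the same paragraph, when it turns to endline, drops both.

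For social support and decision-making the places disagree. A person building the endline questionnaire from the Measures paragraph and Table 3 could take these scales for baseline characteristics. A person reading the Aim 3 analysis would take them for six-month measures. Social support matters most here, because the text component is itself described in Table 2 as social support and the factorial design exists to separate text from voice.

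The pilot is meant to inform the design of a larger trial. If breastfeeding or family planning shows no difference, the team will want to know whether the intermediate targets failed to move, or moved without effect. Endline values that were never collected cannot be recovered later.

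**Working it through.** No arithmetic applies and the plan gives no figure to reproduce. The check traces each construct through every place where it could be scheduled or analysed. Knowledge and mental health, also named in the Significance hypothesis, are included for comparison.

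| Construct | Baseline sentence | Endline sentence | Table 3 | Aim 3 analysis | SAP effectiveness list |
|---|---|---|---|---|---|
| Knowledge | named | named | effectiveness row | main outcome | listed |
| Mental health | not named | named | effectiveness row (depression, anxiety) | named scale | listed |
| Self-efficacy | named | not named | absent | absent | absent |
| Perceived norms | named | not named | absent | absent | absent |
| Social support | not named | not named | sociodemographic row | named scale | absent |
| Decision-making | not named | not named | sociodemographic row | measured as empowerment | absent |

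1. **Self-efficacy and norms.** The only survey that names them is the baseline. Women are recruited in the last month of pregnancy, and the Inclusion of Women and Minorities section says the intervention begins postpartum. A baseline value therefore precedes exposure, assuming baseline is taken at or near enrolment. That leaves no named post-exposure measure for any of the 160 women (40 per arm).

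2. **Does the open ending of the endline list cover them?** The list closes with an et cetera, but what it leaves open is a set of knowledge, behaviour and health questions, and it refers the reader to Table 3. Table 3 contains neither construct.

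3. **Social support and decision-making.** The baseline sentence does not name them. They reach baseline only in two steps: Table 3 classes them as sociodemographic, and the Measures paragraph assigns sociodemographics to baseline. Against that, the Aim 3 analysis places both under a six-month heading, and the hypotheses paragraph is framed around what follows exposure. Intent is therefore stated, but no time point is written beside either scale.

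4. **A possible substitute.** Table 3's acceptability row asks how women value the social support gained from taking part. Control women receive no group, so this item cannot supply a four-arm contrast.

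5. **Change from baseline.** The Aim 3 analysis speaks of arm differences in improvements, and the SAP plots outcomes over time. Both need two measurements. The SAP's regression model contains the two factor indicators and their interaction, with no baseline term.

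Count: two of the four constructs have no named endline measure. The other two are promised for analysis, with conflicting classification and no stated time point.

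**The case against.** The strongest reply concerns social support and decision-making. A reader might infer that all four constructs are confined to baseline, so that the SAP's social-support comparison would rest on values taken before exposure. The documents do not support that. The Aim 3 analysis names a social-support scale in the same sentence as depression and anxiety, and mental health is listed at endline, so joint collection is the natural reading. The hypotheses paragraph also implies a comparison after exposure. This reply stands, and it reduces the problem for these two constructs to a conflict between passages.

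A reader might also infer that the sociodemographic label would lead the analyst to adjust for endline social support and so remove part of the effect. The Protocol says only that relevant sociodemographics will be controlled for as necessary. Nothing says endline values would be used, so this is speculation.

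It can further be said that the study is an unpowered pilot, that no mediation analysis is promised, and that self-efficacy and norms are hypothesised only in the rationale, with no arm comparison promised for either. All true, and this limits the weight of the point. It does not remove the gap: the plan states that the intervention acts on these two constructs, measures them once, and never says that change in them will go unassessed.

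**Conclusion.** The point holds in two parts of unequal strength. Self-efficacy and perceived norms are hypothesised targets with a baseline measure only; under the plan as written, no six-month arm difference in either can be estimated. Social support and decision-making are committed Aim 3 measures, but Table 3's classification, the endline sentence and the SAP effectiveness list do not agree with that commitment and must be reconciled. It would be wrong to say that arm differences in these two cannot be estimated.

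The conclusion assumes that the survey lists are followed literally and that baseline precedes the intervention. Figure 1, which the Protocol cites for targets and outcomes, is not in the text available and could not be checked. This is a worthwhile and inexpensive correction, and it does not undermine the feasibility and acceptability aims.

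**What to change.** - In the Measures paragraph and Table 3, list the self-efficacy items, the perceived-norms items, the social-support scale, and the decision-making and mobility scales at both baseline and endline, with identical wording in all four arms. A time-point column in Table 3 would settle the matter.
- Move social support and decision-making out of the sociodemographic row.
- Add all these measures, labelled exploratory, to the effectiveness paragraph in the Protocol's Statistical Design and Power section and in the SAP.
- Compare arms at endline with the woman's own baseline value of the same scale added as a covariate to the SAP's regression model.
- If the team prefers not to repeat self-efficacy and norms, state that change in them will not be assessed. This keeps the documents consistent but gives up the information.

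The cost is revised wording and a few extra minutes at the endline home interview, which already takes place. No new visit or staff is needed.

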Aim 2. To assess the feasibility and acceptability of the optimized *MeSSSSage* intervention. In Phase 2 we will evaluate the feasibility and acceptability of two intervention components using a controlled 4-arm factorial design (n=160; 40 per arm): 1) real-time mobile voice information and support group alone, 2) asynchronous/on-demand text-based group support only, and 3) real-time mobile voice information and support group plus asynchronous/on-demand text-based group support. Feasibility and acceptability will be assessed via back-end data, surveys, and IDIs with purposively selected participants (n=30) and moderators.

Aim 3. To explore the preliminary effectiveness of the optimized *MeSSSSage* intervention components on six-month maternal and neonatal health outcomes. Phase 2 data will help us develop a preliminary understanding of the impacts of the intervention components on MCH health-related knowledge, behaviors and outcomes including exclusive breastfeeding, immunization, family planning uptake, postnatal visits, mental health and empowerment; however, it is not statistically powered to formally assess effectiveness.

This study is significant and innovative in addressing key priorities of NICHD's Pregnancy and Perinatology Branch and using systematic, user-centered and experience-driven design approach. These results will inform the most acceptable, feasible, and potentially efficacious intervention design to be robustly tested through an R01 mechanism to assess effectiveness for maternal and infant health outcomes, explore other research questions relevant to intervention development and scale-up for postnatal health among South Asian women, and explore generalizability across populations.

Significance

[figure not shown]

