Table 2: *MeSSSSage* components to be tested in feasibility and acceptability assessment (Phase 2).

	Arm 1	Arm 2	Arm 3	Control
Real-time live voice call group meeting: Interactive educational program with scripted didactic component plus discussion/question. Lead and moderated by health professional.	X		X	
Text-based, asynchronous, on-demand social support: App-based small group text-based communication. Moderated by health professional.		X	X	
Standard of care: 3 visits in the first 7 days postnatal (facility and home)	X	X	X	X

Procedures: Unless found not feasible or acceptable within Phase 1 activities, women will be recruited using the approach described above (Aim 1). At the time of enrollment, the study protocol will be described to the women per informed consent procedures. Written confirmation will be obtained from interested women and their phone numbers will be collected (and tested). Women without a phone will be provided with a phone and all participants' airtime will be covered for the length of the 6-month research project. Women who consent will be randomly enrolled into 1 of the 4 study arms using a random number generator. We will test each study condition using 2 groups of women, with intervention initiation staggered 1 month apart. Women in the control group will receive the standard of care. All women will be given 50 Indian Rupees for participation in each session (in addition to airtime and phone if needed), and ASHAs will receive 150 Indian Rupees for moderating each session. Assessment of feasibility and acceptability (Aim 2) and preliminary effectiveness (Aim 3) will be accomplished using mixed-methods including quantitative surveys, in-depth interviews, and technology assessment.

Survey data collection: Baseline and endline surveys will be administered by a research assistant in the respondent's home. Endline survey will be collected roughly 6 months postnatal, after potential participation in ~24 *MeSSSSage* sessions (details to be determined during Phase 1). We will capture women's health record cards and ASHA registers to validate self-reported health outcome data. Data will be collected on a tablet using the secure REDCap mobile research administration app, stored in a password protected database at UCSF, and no identifiable information will be included with analytic datasets (identifiable data will be stored separately).

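### Depression and anxiety are effectiveness outcomes, but the listed baseline survey has no measure of them, so no plot over time and no baseline adjustment is possible as written

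*Protocol*

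**What the plan says.** **Baseline.** Protocol, Approach, Phase 2, Measures: "The baseline survey content will include sociodemographic characteristics and knowledge about maternal and infant health, self-efficacy, and perceived social norms". No depression or anxiety scale is listed.

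**Endline.** The next sentence gives the endline content, which covers "immunization, family planning uptake, maternal physical and mental health, etc. which have previously been used in this setting".

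**Status of the outcome.** Table 3 of the protocol has a row for effectiveness health outcomes: "Early childhood immunization, postnatal depression and anxiety, postnatal family planning adoption". The table gives no time points. The Aim 3 analysis text offers the Hopkins Symptom Checklist as an example instrument and does not say when it is given.

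**Promised analysis.** Protocol, Analysis, Aim 3: "we will statistically evaluate differences by study arm in improvements in women's knowledge, behaviors, and maternal and child health outcomes", relative to control. The SAP, under its hypotheses for the exploratory effectiveness analyses, plans plots over time to describe "overall patterns of change across time in the outcomes for the intervention and control groups".

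**Model.** The SAP regression contains an intercept, voice, text and their product, with no covariate. The protocol's Aim 3 text allows adjustment for socio-demographics where needed, but does not mention a baseline value of the outcome.

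**Design.** The protocol describes Phase 2 as "using a controlled 4-arm factorial design (n=160; 40 per arm"). On allocation it says "Women who consent will be randomly enrolled into 1 of the 4 study arms using a random number generator"; no stratification is described.

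**The concern.** The plan speaks of improvement and of change over time, and both suggest at least two measurements. Knowledge is listed at both surveys. Mental health is listed at one. If the lists are followed as written, the SAP's plot over time cannot be drawn for depression and anxiety, and the analyst has no pre-intervention symptom score to use as a covariate.

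The covariate matters because the pilot is meant to show the direction of effects ahead of a larger trial, using arms of 40. A baseline symptom score would probably be among the better available predictors of the endline score, and it cannot be collected afterwards.

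**Working it through.** **Inputs.** 160 women and 40 per arm (protocol, Aim 2). The documents give no standard deviation, dropout rate or baseline-endline correlation r. I work in SD units, assume equal variance at the two surveys, and take r = 0.3, 0.5 and 0.6. Clustering by support group and dropout are ignored.

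**Plan's own figure.** 4 arms × 40 = 160, which reproduces. There is no power calculation to check.

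**Endline-only contrast.** With 0/1 indicators, the SAP's voice and text coefficients each compare one arm of 40 with control.
- SE = √(2/40) = 0.224 SD.
- 95% half-width = 1.96 × 0.2236 = 0.438 SD.

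**Baseline score as covariate.** SE = √(2/40) × √(1 − r²). Nominal equivalent number per arm = 40/(1 − r²).

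**Change score.** SE = √(2/40) × √(2(1 − r)).

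| r | Variance cut, r² | SE, covariate | 95% half-width, covariate | Equivalent n per arm | SE, change score |
|---|---|---|---|---|---|
| 0.3 | 9% | 0.213 | 0.418 | 44 | 0.265 |
| 0.5 | 25% | 0.194 | 0.380 | 53 | 0.224 |
| 0.6 | 36% | 0.179 | 0.351 | 62.5 | 0.200 |

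The change score beats endline-only only if 2(1 − r) < 1, that is r > 0.5. Below that it is worse than having no baseline at all (0.265 against 0.224 at r = 0.3). The covariate analysis is never worse than the change score, since 1 − r² ≤ 2(1 − r) whenever r ≤ 1.

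**Chance imbalance.** The baseline difference between two arms also has SE 0.224 SD. The probability that it exceeds 0.2 SD in either direction is 2 × (1 − Φ(0.2/0.2236)) = 0.37. A baseline difference d moves the endline contrast by r × d, so 0.2 SD moves it by:
- 0.3 × 0.2 = 0.06 SD
- 0.5 × 0.2 = 0.10 SD
- 0.6 × 0.2 = 0.12 SD

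This movement is already part of the 0.224 SD standard error. It is the same loss as the wider interval, seen from another side, and should not be added to it.

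**What this means for reading direction.** Suppose the true effect is 0.2 SD (an illustration, not a figure from the plan). The endline-only estimate has the wrong sign with probability Φ(−0.2/0.2236) = 19%. With the covariate at r = 0.5 it is Φ(−0.2/0.1936) = 15%.

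**The case against.** Three stronger readings are tempting, and the documents support none of them.

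**That the scale is definitely given only at endline.** This is an inference from the content lists. The baseline sentence says what the survey will include, which need not be everything, and Table 3 assigns no time points. Table 3 also places social support, which the Aim 3 text pairs with mental health, among the sociodemographic items, a category that is collected at baseline. What can be said is that nothing in either document places a depression or anxiety scale at baseline.

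**That the promised analysis cannot be run.** The only specified model regresses the outcome on the two factors and their product. It contains no change term and runs on endline data. The Aim 3 phrase "we will statistically evaluate differences by study arm in improvements in" covers all outcomes together, and several of them (exclusive breastfeeding at six months, immunization, postnatal family planning) have no value before birth. For those it can only mean an endline difference between arms, and it may mean the same here. Only the SAP's plot over time strictly needs two measurements.

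**That chance imbalance is left uncorrected and biases the result.** Randomisation keeps the endline contrast unbiased, and its confidence interval already allows for imbalance. The 37% figure is the chance of a baseline difference, not of an error of that size. The optional socio-demographic adjustment could also recover a little, although it is absent from the SAP model.

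It is also fair to say that the stakes are low: depression and anxiety are not among the main outcomes named under Aim 3, and significance testing is deliberately played down. All of these objections stand. They leave intact the missing baseline measure, the plot that cannot be drawn, and an inexpensive gain in precision.

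**Conclusion.** The point holds as a low-priority improvement. As listed, the surveys do not provide a depression or anxiety score before the intervention, so the SAP's plot over time cannot be produced for this outcome and baseline adjustment is not possible. The endline-only factorial regression remains valid.

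The gain from a baseline covariate is precision alone: a variance cut of 9% to 36%, with 25% as the mid case. The size depends on the assumed correlation, and the equivalent sample sizes are nominal because two groups per condition and any dropout are left out. At the lower end the gain is small.

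A score taken in late pregnancy is a starting level of symptoms, not postnatal depression. It serves as a covariate and as the first point on a plot. That the baseline survey precedes birth is itself inferred from enrolment in the final month of pregnancy.

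**What to change.** 1. In the protocol's Measures section and Table 3, state the time point of each scale. If a baseline depression and anxiety measure is already intended, one sentence settles this part.
2. Otherwise, add to the existing baseline home survey whichever scale will be used at endline. The Hopkins Symptom Checklist is only an example in the protocol, so name the instrument and use the same items both times.
3. In the SAP, for this outcome, add the baseline score to the model: yᵢ = β₀ + β₁Z₁ᵢ + β₂Z₂ᵢ + β₃Z₁ᵢZ₂ᵢ + γ·baselineᵢ + εᵢ. Do not use a change score as the analysis variable.
4. Limit the SAP's statement about plots over time to outcomes measured at both surveys.

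**Cost.** A few more minutes per woman at a visit that already takes place (my estimate; the documents give no survey length), and one residual degree of freedom (160 − 4 = 156 becomes 155 with complete data). The protocol already describes referral for participants in distress. The change has to be made before baseline collection starts, because a missed baseline score cannot be recovered.
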